Ataxia	Asymptomatic ataxia detectable on exam OR Minimal ataxia causing no or minimal interference with usual social & functional activities	Symptomatic ataxia causing greater than minimal interference with usual social & functional activities	Symptomatic ataxia causing inability to perform usual social & functional activities	Disabling ataxia causing inability to perform basic self-care functions
Cognitive and Behavioral/Attentional Disturbance (including dementia and Attention Deficit Disorder)	Disability causing no or minimal interference with usual social & functional activities OR Specialized resources not indicated	Disability causing greater than minimal interference with usual social & functional activities OR Specialized resources on part-time basis indicated	Disability causing inability to perform usual social & functional activities OR Specialized resources on a full-time basis indicated	Disability causing inability to perform basic self-care functions OR Institutionalization indicated
CNS Ischemia (acute)	NA	NA	Transient ischemic attack	Cerebral vascular accident (CVA, stroke) with neurological deficit

NEUROLOGICAL				
	Grade 1	Grade 2	Grade 3	Grade 4
Developmental delay – Pediatric ≤ 16 Years	Mild developmental delay, either motor or cognitive, as determined by comparison with a developmental screening tool appropriate for the setting	Moderate developmental delay, either motor or cognitive, as determined by comparison with a developmental screening tool appropriate for the setting	Severe developmental delay, either motor or cognitive, as determined by comparison with a developmental screening tool appropriate for the setting	Developmental regression, either motor or cognitive, as determined by comparison with a developmental screening tool appropriate for the setting
Headache	Symptoms causing no or minimal interference with usual social & functional activities	Symptoms causing greater than minimal interference with usual social & functional activities	Symptoms causing inability to perform usual social & functional activities	Symptoms causing inability to perform basic self-care functions OR Hospitalization indicated (other than ER visit) OR Headache with significant impairment of alertness or other neurologic function
Insomnia	NA	Difficulty sleeping causing greater than minimal interference with usual social/functional activities	Difficulty sleeping causing inability to perform usual social & functional activities	Disabling insomnia causing inability to perform basic self-care functions
Neuromuscular Weakness (including myopathy & neuropathy)	Asymptomatic with decreased strength on exam OR Minimal muscle weakness causing no or minimal interference with usual social & functional activities	Muscle weakness causing greater than minimal interference with usual social & functional activities	Muscle weakness causing inability to perform usual social & functional activities	Disabling muscle weakness causing inability to perform basic self-care functions OR Respiratory muscle weakness impairing ventilation
Neurosensory Alteration (including paresthesia and painful neuropathy)	Asymptomatic with sensory alteration on exam or minimal paresthesia causing no or minimal interference with usual social & functional activities	Sensory alteration or paresthesia causing greater than minimal interference with usual social & functional activities	Sensory alteration or paresthesia causing inability to perform usual social & functional activities	Disabling sensory alteration or paresthesia causing inability to perform basic self-care functions

NEUROLOGICAL				
	Grade 1	Grade 2	Grade 3	Grade 4
Seizure: (new onset)	NA	1 seizure	2–4 seizures	Seizures of any kind that are prolonged, repetitive (eg, status epilepticus), or difficult to control (eg, refractory epilepsy)
Seizure: (pre-existing) For Worsening of Existing Epilepsy the Grades Should Be Based on an Increase from Previous Level of Control to Any of These Levels	NA	Increased frequency of pre-existing seizures (non-repetitive) without change in seizure character OR infrequent breakthrough seizures while on stable meds in a previously controlled seizure disorder	Change in seizure character from baseline either in duration or quality (eg, severity or focality)	Seizures of any kind that are prolonged, repetitive (eg, status epilepticus), or difficult to control (eg, refractory epilepsy)
Seizure – Pediatric < 18 Years	Seizure, generalized onset with or without secondary generalization, lasting < 5 minutes with < 24 hours post ictal state	Seizure, generalized onset with or without secondary generalization, lasting 5–20 minutes with < 24 hours post ictal state	Seizure, generalized onset with or without secondary generalization, lasting > 20 minutes	Seizure, generalized onset with or without secondary generalization, requiring intubation and sedation
Syncope (not associated with a procedure)	NA	Present	NA	NA
Vertigo	Vertigo causing no or minimal interference with usual social & functional activities	Vertigo causing greater than minimal interference with usual social & functional activities	Vertigo causing inability to perform usual social & functional activities	Disabling vertigo causing inability to perform basic self-care functions

MUSCULOSKELETAL				
	Grade 1	Grade 2	Grade 3	Grade 4
Arthralgia See also Arthritis	Joint pain causing no or minimal interference with usual social & functional activities	Joint pain causing greater than minimal interference with usual social & functional activities	Joint pain causing inability to perform usual social & functional activities	Disabling joint pain causing inability to perform basic self-care functions
Arthritis See also Arthralgia	Stiffness or joint swelling causing no or minimal interference with usual social & functional activities	Stiffness or joint swelling causing greater than minimal interference with usual social & functional activities	Stiffness or joint swelling causing inability to perform usual social & functional activities	Disabling joint stiffness or swelling causing inability to perform basic self-care functions
Bone Mineral Loss Pediatric < 21 Years	BMD t-score or z-score -2.5 to -1.0 BMD z-score -2.5 to -1.0	BMD t-score or z-score < -2.5 BMD z-score < -2.5	Pathological fracture (including loss of vertebral height) Pathological fracture (including loss of vertebral height)	Pathologic fracture causing life-threatening consequences Pathologic fracture causing life-threatening consequences
Myalgia (non-injection site)	Muscle pain causing no or minimal interference with usual social & functional activities	Muscle pain causing greater than minimal interference with usual social & functional activities	Muscle pain causing inability to perform usual social & functional activities	Disabling muscle pain causing inability to perform basic self-care functions
Osteonecrosis	NA	Asymptomatic with radiographic findings AND No operative intervention indicated	Symptomatic bone pain with radiographic findings OR Operative intervention indicated	Disabling bone pain with radiographic findings causing inability to perform basic self-care functions

SYSTEMIC				
	Grade 1	Grade 2	Grade 3	Grade 4
Acute Systemic Allergic Reaction	Localized urticaria (wheals) with no medical intervention indicated	Localized urticaria with medical intervention indicated OR Mild angioedema with no medical intervention indicated	Generalized urticaria OR Angioedema with medical intervention indicated OR Symptomatic mild bronchospasm	Acute anaphylaxis OR Life-threatening bronchospasm OR laryngeal edema
Chills	Symptoms causing no or minimal interference with usual social & functional activities	Symptoms causing greater than minimal interference with usual social & functional activities	Symptoms causing inability to perform usual social & functional activities	NA
Fatigue Malaise	Symptoms causing no or minimal interference with usual social & functional activities	Symptoms causing greater than minimal interference with usual social & functional activities	Symptoms causing inability to perform usual social & functional activities	Incapacitating fatigue/malaise symptoms causing inability to perform basic self-care functions
Fever (nonaxillary)	37.7°C to 38.6°C 99.8°F to 101.5°F	38.7°C to 39.3°C 101.6°F to 102.8°F	39.4°C to 40.5°C 102.9°F to 104.9°F	> 40.5°C > 104.9°F
Pain- Indicate Body Site See also Injection Site Pain, Headache, Arthralgia, and Myalgia	Pain causing no or minimal interference with usual social & functional activities	Pain causing greater than minimal interference with usual social & functional activities	Pain causing inability to perform usual social & functional activities	Disabling pain causing inability to perform basic self-care functions OR Hospitalization (other than ER visit) indicated
Unintentional Weight Loss	NA	5% to 9% loss in body weight from baseline	10% to 19% loss in body weight from baseline	≥ 20% loss in body weight from baseline OR Aggressive intervention indicated [eg, tube feeding or total parenteral nutrition]

INJECTION SITE REACTION				
	Grade 1	Grade 2	Grade 3	Grade 4
Injection Site Pain (pain without touching) Or Tenderness (pain when area is touched)	Pain/tenderness causing no or minimal limitation of use of limb	Pain/tenderness limiting use of limb OR Pain/tenderness causing greater than minimal interference with usual social & functional activities	Pain/tenderness causing inability to perform usual social & functional activities	Pain/tenderness causing inability to perform basic self-care function OR Hospitalization (other than ER visit) indicated for management of pain/tenderness
Injection Site Reaction (Localized), > 15 Years Pediatric ≤ 15 Years	Erythema OR Induration of 5 × 5 cm to 9 × 9 cm (or 25–81 × cm ²) Erythema OR Induration OR Edema present but ≤ 2.5 cm diameter	Erythema OR Induration OR Edema > 9 cm any diameter (or > 81 cm ²) Erythema OR Induration OR Edema > 2.5 cm diameter but < 50% surface area of the extremity segment (eg, upper arm/thigh)	Ulceration OR Secondary infection OR Phlebitis OR Sterile abscess OR Drainage Erythema OR Induration OR Edema involving ≥ 50% surface area of the extremity segment (eg, upper arm/thigh) OR Ulceration OR Secondary infection OR Phlebitis OR Sterile abscess OR Drainage	Necrosis (involving dermis and deeper tissue) Necrosis (involving dermis and deeper tissue)
Pruritis Associated with Injection See also Skin: Pruritis (itching—no skin lesions)	Itching localized to injection site AND Relieved spontaneously or with < 48 h treatment	Itching beyond the injection site but not generalized OR Itching localized to injection site requiring ≥ 48 h treatment	Generalized itching causing inability to perform usual social & functional activities	NA

ENDOCRINE/METABOLIC				
	Grade 1	Grade 2	Grade 3	Grade 4
Lipodystrophy (eg, back of neck, breasts, abdomen)	Detectable by study participant or caregiver (for young children and disabled adults)	Detectable on physical exam by health care provider	Disfiguring OR Obvious changes on casual visual inspection	NA
Diabetes Mellitus	NA	New onset without need to initiate medication OR Modification of current meds to regain glucose control	New onset with initiation of indicated med OR Diabetes uncontrolled despite treatment modification	Life-threatening consequences (eg, ketoacidosis, hyperosmolar non-ketotic coma)
Gynecomastia	Detectable by study participant or caregiver (for young children and disabled adults)	Detectable on physical exam by health care provider	Disfiguring OR Obvious on casual visual inspection	NA
Hyperthyroidism	Asymptomatic	Symptomatic causing greater than minimal interference with usual social & functional activities OR Thyroid suppression therapy indicated	Symptoms causing inability to perform usual social & functional activities OR Uncontrolled despite treatment modification	Life-threatening consequences (eg, thyroid storm)
Hypothyroidism	Asymptomatic	Symptomatic causing greater than minimal interference with usual social & functional activities OR Thyroid replacement therapy indicated	Symptoms causing inability to perform usual social & functional activities OR Uncontrolled despite treatment modification	Life-threatening consequences (eg, myxedema coma)
Lipoatrophy (eg, fat loss from the face, extremities, buttocks)	Detectable by study participant or caregiver (for young children and disabled adults)	Detectable on physical exam by health care provider	Disfiguring OR Obvious on casual visual inspection	NA

GENITOURINARY				
	Grade 1	Grade 2	Grade 3	Grade 4
Intermenstrual Bleeding (IMB)	Spotting observed by participant OR Minimal blood observed during clinical or colposcopic exam	Intermenstrual bleeding not greater in duration or amount than usual menstrual cycle	Intermenstrual bleeding greater in duration or amount than usual menstrual cycle	Hemorrhage with life-threatening hypotension OR Operative intervention indicated
Urinary Tract obstruction (eg, stone)	NA	Signs or symptoms of urinary tract obstruction without hydronephrosis or renal dysfunction	Signs or symptoms of urinary tract obstruction with hydronephrosis or renal dysfunction	Obstruction causing life-threatening consequences

INFECTION				
	Grade 1	Grade 2	Grade 3	Grade 4
Infection (any other than HIV infection)	Localized, no systemic antiꞵbial treatment indicated AND Symptoms causing no or minimal interference with usual social & functional activities	Systemic antiꞵbial treatment indicated OR Symptoms causing greater than minimal interference with usual social & functional activities	Systemic antiꞵbial treatment indicated AND Symptoms causing inability to perform usual social & functional activities OR Operative intervention (other than simple incision and drainage) indicated	Life-threatening consequences (eg, septic shock)

Basic Self-care Functions: Activities such as bathing, dressing, toileting, transfer/movement, continence, and feeding.

Usual Social & Functional Activities: Adaptive tasks and desirable activities, such as going to work, shopping, cooking, use of transportation, pursuing a hobby, etc

Appendix 4. Pregnancy Precautions, Definition for Female of Childbearing Potential, and Contraceptive Requirements

1) Background

Non-clinical toxicity studies of sofosbuvir and ledipasvir demonstrated no adverse effect on embryo-fetal development. However, there are no clinical studies of sofosbuvir or ledipasvir in pregnant women. Please refer to the latest version of the investigator's brochure for additional information.

2) Definition of Female of Childbearing Potential and Contraceptive Requirements for Female Subjects (and their male partners)

Women > 54 years of age with cessation for ≥ 12 months of previously occurring menses, or women of any age who have had a hysterectomy, or have had both ovaries removed, or have had medically documented ovarian failure will be considered to be of non-childbearing potential.

Women ≤ 54 years of age (including those with amenorrhea of any duration) who have not had a hysterectomy, and have not had both ovaries removed, and have not had medically documented ovarian failure will be considered to be of childbearing potential.

Women of childbearing potential must have a negative serum pregnancy test at Screening and a negative urine pregnancy test on the Baseline/Day 1 visit prior to randomization. They must also agree to one of the following from 3 weeks prior to Baseline/Day 1 until 30 days after last dose of study drug.

- Complete abstinence from intercourse. Periodic abstinence (e.g., calendar, ovulation, symptothermal, post-ovulation methods) is not permitted.

Or

- Consistent and correct use of 1 of the following methods of birth control listed below, in addition to a male partner who correctly uses a condom, from the date of Screening until 30 days after last dose of study drug:
 - intrauterine device (IUD) with a failure rate of < 1% per year
 - female barrier method: cervical cap or diaphragm with spermicidal agent
 - tubal sterilization
 - vasectomy in male partner
 - hormone-containing contraceptive:
 - implants of levonorgestrel

- injectable progesterone
- oral contraceptives (either combined or progesterone only)
- contraceptive vaginal ring
- transdermal contraceptive patch

3) Contraceptive Requirements for Male Subjects (and their female partners)

All male study participants must agree to consistently and correctly use a condom from the date of Screening until 90 days after the last dose of study drug. If their female partner is of child bearing potential (as defined above), their female partner must use 1 of the methods of birth control listed above from the date of Screening until 90 days after the last dose of study drug.

Male subjects must agree to refrain from sperm donation for at least 90 days after the last dose of study drug.

4) Procedures to be Followed in the Event of Pregnancy

Subjects will be instructed to notify the investigator if they (or their partner) become pregnant at any time during the study, or if they become pregnant within 30 days (90 days for partners of male subjects) of last study drug dose. Subjects who become pregnant or who suspect that they are pregnant must report the information to the investigator and discontinue study drug immediately. Subjects whose partner has become pregnant or suspects she is pregnant must report the information to the investigator.

Instructions for reporting pregnancy, partner pregnancy, and pregnancy outcome are outlined in Section [7.7.2.1](#).

Appendix 5. Calculation of Historical Control SVR12 for Treatment-naïve Korean Subjects and for Treatment-naïve Chinese Subjects with Chronic GT-1 HCV Infection

This section details the calculation for the historical control SVR12 rates for treatment-naïve Korean subjects and for treatment-naïve Chinese subjects with chronic GT-1 HCV infection.

The historical control calculation for Korea assumes that of the treatment-naïve subjects with HCV GT-1 infection to be enrolled in Korea, approximately 60% will have ‘Uncomplicated Infection’, ~30% will be ‘Elderly’, and ~10% will be ‘Cirrhotic’. Based on discussions with clinical investigators in these countries, these assumptions ensure a conservative estimation of the historical SVR rate following Peg-IFN α +RBV in the respective populations. The references used for the calculation of the historical control rates are provided in [Appendix Table 2](#) below.

For Korea, the SVR rates among each of the three patient populations are calculated according to the reference studies ([Appendix Table 2](#)). The overall historical SVR rate is subsequently calculated as the weighted average of the population-specific rates, with the weight being the expected percentages of patients in each population. With these assumptions in mind and using the referenced literature, the adjusted historical SVR control rate for the populations in Korea are calculated as follows:

Appendix Table 1. SVR rates following Peg-IFN α +RBV in Treatment-Naïve Korean Subjects with GT-1 HCV Infection

Country	Uncomplicated Infection	Elderly	Cirrhotic	Weighted Average
Korea	62.7%	30.8%	24%	$62.7\% * 0.6 + 30.8\% * 0.3 + 24\% * 0.1 = 49\%$

Therefore, a null adjusted historical SVR rate for this study is 49% following estimation of the SVR rate for Korea.

For China, the historical control rate has been calculated according to the reference studies in [Appendix Table 3](#). SVR rates are not reported separately for elderly patients or those with cirrhosis in these references. Consequently, the calculated historical SVR rate of 57% has not been adjusted by different population.

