4. SUBJECT POPULATION

4.1. Number of Subjects and Subject Selection

Approximately 360 subjects will be enrolled in this study with approximately 180 treatment-naïve subjects and approximately 180 treatment-experienced subjects. Up to 20% of subjects enrolled in the study may have compensated cirrhosis at screening.

In order to manage the total study enrollment, Gilead Sciences, Inc., at its sole discretion, may suspend screening and/or enrollment at any site or study-wide at any time.

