8.5. Efficacy Analysis

8.5.1. Primary Analysis

The primary efficacy endpoint is SVR12 (HCV RNA <LLOQ 12 weeks after discontinuation of therapy) in the FAS population. The primary analysis will be performed after all enrolled subjects have been followed through 12 weeks post-treatment or discontinued from study.

The primary efficacy analysis described below will compare the observed SVR12 rate for the investigational regimen (i.e., SOF/LDV FDC for 12 weeks) versus the historical SVR null rate in treatment-naïve Korean subjects and in treatment-naïve Chinese subjects, respectively.

In addition, a point estimate with a two-sided 95% exact confidence interval using the binomial distribution (Clopper-Pearson method) {20839} will be constructed for the SVR12 rate by treatment-naïve and treatment-experienced subjects for each region (i.e., China, Korea or Taiwan), Korea plus Taiwan and overall (i.e., China plus Korea plus Taiwan).

Treatment-Naïve Subjects

In the primary efficacy analysis the SVR12 rate from Korea and China will be compared to the adjusted historical SVR null rate of 49% in Korea and historical control rate of 57% in China, respectively (as calculated in [Appendix 5](#)) using a two-sided exact one-sample binomial test.

The hypothesis for superiority in Korea is:

- H0: SVR12 rate = 49%,
- H1: SVR12 rate \neq 49%.

The hypothesis for superiority in China is:

- H0: SVR12 rate = 57%,
- H1: SVR12 rate \neq 57%.

Treatment-Experienced Subjects

There is no treatment option available in China, Korea or Taiwan for treatment-experienced patients with GT-1 infection. In the absence of effective antiviral therapy, spontaneous clearance of the HCV is rare. Consequently a nominal SVR rate of 5% is assumed for treatment-experienced subjects.

No statistical hypothesis testing will be performed in treatment-experienced subjects. For each region (i.e., China, Korea or Taiwan), Korea plus Taiwan, and overall (i.e., China plus Korea plus Taiwan), a point-estimate with two-sided 95% exact confidence interval using the binomial distribution (Clopper-Pearson method) will be constructed for the SVR12 rate.

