Appendix Table 2. Literature References for Historical Control Rate Calculations in Korea

SVR Rates in Korea			
Population	SVR%	SVR n/N	Reference
GT-1 Treatment Naïve (Peg-IFN/RBV 48 Weeks)	80.8	21/26	{24236}
	54.7	58/106	{24236}
	62.7	341/543	{26807}
	62.2	158/254	{26389}
	64.2	104/162	{26389}
	66.0	31/47	{26390}
Overall SVR Rate	62.7%		
SVR Rates in Korea Elderly			
Population	SVR%	SVR n/N	Reference
GT-1 Treatment Naïve (Peg-IFN/RBV 48 weeks)	30.8	4/13	{26390}
Overall SVR Rate	30.8%		
SVR Rates in Korea Cirrhotics			
Population	SVR%	SVR n/N	Reference
GT-1 Treatment Naïve (Peg-IFN/RBV 48 weeks)	24.0	12/50	{24405}
Overall SVR Rate	24.0%		

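### Does Korea's fixed 49% null need re-weighting because it rests on an assumed 60/30/10 case mix and a 4/13 elderly rate?

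*Protocol*

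**What the plan says.** Protocol Appendix 5 describes the Korean treatment-naïve population it expects. Of the subjects "to be enrolled in Korea, approximately 60% will have" uncomplicated infection, with about 30% elderly and 10% cirrhotic making up the rest. The null is the average of three literature rates, "with the weight being the expected percentages of patients in each population". Appendix Table 2 gives those rates as 62.7% (six pooled rows), 30.8% (4/13, under the heading "SVR Rates in Korea Elderly") and 24.0% (12/50). The appendix says that "these assumptions ensure a conservative estimation of the historical SVR rate". It concludes: "Therefore, a null adjusted historical SVR rate for this study is 49% following estimation of the SVR rate for Korea".

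Protocol 8.5.1 fixes the test: "the SVR12 rate from Korea and China will be compared to the adjusted historical SVR null rate of 49% in Korea". The same section plans an exact confidence interval "for the SVR12 rate by treatment-naïve and treatment-experienced subjects for each region". The only stated control on case mix is in Protocol 4.1: "Up to 20% of subjects enrolled in the study may have compensated cirrhosis at screening". There is no quota by age.

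The supplied SAP (section 6.1.2) tests Chinese treatment-naïve subjects only. SAP section 1 says that Korea and Taiwan were analysed under a SAP dated 22 July 2014 and reported in an interim CSR dated 10 October 2014. That SAP is not among the documents.

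**The concern.** In a study without a control arm, the historical rate carries the whole superiority claim. Here it depends on a forecast of who enrols. If the Korean cohort turns out younger or less cirrhotic than 60/30/10, the same patients on the old regimen would have had an SVR above 49%, and the test would be easier to pass than its nominal level implies. The elderly rate carries 30% of the weight but comes from 13 patients and is used as if known exactly. The claim of conservatism therefore looks stronger than its support. The possible harm is a superiority claim for Korea that partly reflects a null set too low.

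**Working it through.** **Inputs.** n = 40, null 49%, improvement 27 points (so 49% + 27% = 76%), two-sided alpha 0.05, exact binomial (Protocol 8.8 and 8.5.1). Stratum rates and weights are from Appendix 5. The pass mark is not printed. I take it as the smallest count above 40 × p0 whose upper-tail probability is at most 0.025. Ordering outcomes by their probability instead gives the same mark for every case mix listed below.

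**The plan's own figures.**
- Uncomplicated pool: (21+58+341+158+104+31)/(26+106+543+254+162+47) = 713/1138 = 62.65%, stated as 62.7%.
- Weighted null: 0.627×0.6 + 0.308×0.3 + 0.24×0.1 = 0.4926, stated as 49%.
- At p0 = 0.49: P(X≥26) = 3.05% and P(X≥27) = 1.40%, so the mark is 27/40.
- Power at 76%: P(X≥27) = 92.2%. The stated power of at least 90% holds.

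**Changing the mix.** With E elderly and C cirrhotic of 40, p0 = [0.627(40−E−C) + 0.308E + 0.24C]/40. The mixes other than 12/4 are assumptions.

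| Elderly / cirrhotic | p0 | P(X≥26) | P(X≥27) | Mark |
|---|---|---|---|---|
| 12 / 4 (planned) | 49.26% | 3.29% | 1.53% | 27 |
| 10 / 4 | 50.85% | 5.06% | 2.49% | 27 |
| 9 / 4 | 51.65% | 6.20% | 3.13% | 28 |
| 9 / 6 | 49.72% | 3.73% | 1.76% | 27 |
| 9 / 8 | 47.78% | 2.13% | 0.94% | 26 |
| 14 / 4 | 47.66% | 2.06% | 0.90% | 26 |

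A shortfall of three elderly subjects, with cirrhosis held at 4, raises the mark by one. The upper-tail error at 27 would then be 3.13%, against 2.5%. Two extra elderly subjects, or four extra cirrhotic ones alongside that shortfall, lower the mark by one.

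**Uncertainty in 4/13.** The exact 95% interval is 9.1% to 61.4%. At 60/30/10:
- lower limit: 0.3762 + 0.3×0.0909 + 0.024 = 42.7%, mark 24;
- upper limit: 0.3762 + 0.3×0.6143 + 0.024 = 58.4%, mark 30.

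**Does it matter at a plausible SVR12?** Protocol 1.3 cites rates above 93% in treatment-naïve subjects on this regimen, and 100% of 83 in Japan.

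| Mark | Reached at 76% | at 90% | at 93% |
|---|---|---|---|
| 27 | 92.2% | >99.99% | >99.99% |
| 28 | 85.8% | 99.99% | >99.99% |
| 30 | 64.1% | 99.85% | 99.99% |
| 32 | 35.2% | 98.45% | 99.85% |

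The mark of 32 is what a null of 62.7% would require, with no allowance for elderly or cirrhotic subjects at all. The mark of 30 is the one at the upper limit for 4/13.

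**The case for a change.** The best case for acting starts from the protocol's own background. Protocol 1.1.2 gives Korean treatment-naïve SVR rates of 55–70% in trials and 55% (58/106) in practice, all above 49%, so the downward adjustment does all the work. Protocol 1.1.3 cites 51.9% in Taiwanese patients aged 65 or over, against 30.8% used for Korea. Put into the formula for illustration, that gives 0.3762 + 0.3×0.519 + 0.024 = 55.6% and a mark of 29, with power at 76% of 76.4%. A small table and one labelled sensitivity test would cost little and would let a reader judge the claim at the enrolled mix.

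Some of this stands. The word for certainty in the conservatism sentence is stronger than 13 patients can support, and Appendix 5 gives no rule for a subject who is both elderly and cirrhotic. But the background also points the other way. Protocol 1.1.2 says most Koreans with chronic hepatitis C are elderly, so a 30% elderly weight leans towards a higher, stricter null. The assumed 10% cirrhosis is half the study-wide cap. Trial entrants may be younger than patients at large, so this does not prove conservatism, but it gives the sentence a basis.

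The proposed analysis would also not settle the matter. It would still use 4/13, the largest source of uncertainty. It would treat 62.7% as a rate for uncomplicated disease, although Appendix Table 2 labels those rows only as treatment-naïve genotype 1. Because Korean results were reported in 2014, it would be chosen with the outcome known.

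**Conclusion.** No change follows. A fixed, pre-specified null with its strata, weights, rates and sources all disclosed is an ordinary choice for a single-arm test, and this one reproduces both its own value and its stated power. The case-mix assumption moves the derived mark by about one subject either way for plausible departures. The 4/13 interval moves it from 24 to 30. Either could matter if SVR12 fell near the 76% planning value; neither is material near the 93% the protocol cites.

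This rests on the regimen performing in Korea roughly as it did in the cited trials, and on reading the 27% improvement as percentage points, which is needed to reproduce the power. The absence of re-weighting is established only for the supplied documents; the 22 July 2014 SAP may address it.

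If the report gives the Korean treatment-naïve elderly and cirrhotic shares, a reader can place the weighted null from the formula above beside the Korean exact interval already planned in Protocol 8.5.1. That is an optional, post hoc reporting note. The primary test, the sample size and the stated power can stay as they are.
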